8. STATISTICAL METHODOLOGY AND STATISTICAL ANALYSES

Continuous variables will be summarized by the number (N), mean, median, standard deviation, minimum and maximum. Categorical variables will be summarized by percent and counts. All summaries will be displayed by treatment. Efficacy data will be listed, tabulated and graphically represented, as appropriate.

All analyses will be based on the full analysis set (FAS) which includes all enrolled subjects who have received at least one dose of study drug.

Below is outlining the definition of baseline for secondary endpoints :

As per Figure 1 below shows each treatment period has been divided into 16 week intervals. Endpoint is the change from the baseline to the subsequent 16th week.

A placebo group is constructed by combining the 3 cohort's running periods. Each cohort has an initial 16 week running period, they are combined together to form a placebo group which will be used as a comparison group, testing against active treatments. There will be a total of 20 subjects in the placebo group.

For cohort 1 the first comparison would be : placebo (3 cohort's running periods) vs. active treatment (1^{st} interval) which starts from the end of the running period to the end of the first 16 weeks of active treatment i.e. week 17 to week 32. The next comparison would be placebo

vs. active treatment (second interval) which starts from the end of the second 16 week active treatment i.e. week 33 to week 48. Then the next comparison would be placebo vs. active treatment (third interval) i.e. week 49 to week 64. Finally comparing placebo vs. active treatment (fourth interval) i.e. week 65 to week 80, as shown in the table 1 below.

The above rational is to be used for cohorts 2 and 3.

To conclude there will be 8 statistical tests.

Active treatment Intervals				
Cohort 1	Cohort 2	Cohort 3		
17-32	17-32	17-32		
33-48	33-48	33-48		
49-64				
65-80				

[figure not shown]

Figure 1. LGMD2i Active vs. "Placebo"

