8.1. Statistical Methods

The planned statistical methods and analyses for the primary and all secondary endpoints are described in detail in Section 8.2.1 and Section 8.2.2 below.

To explore the data further and to assess the goodness-of-fit of all statistical models, separate SAS datasets will be provided by the clinical programmer to the statistician. Covariates for data exploration may include baseline and/or demographic covariates such as gender, age, weight (continuous and/or Pfizer standard categorical cut-offs), site, country, etc.

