8.2.2. Secondary Analyses

The secondary endpoints, change from baseline in FVC, muscle strength, timed function tests and patient reported outcome measures, will be analyzed based on the FAS using a mixed effects model with REML estimation. The change over the lead-in period, treatment, time and treatment by time interaction and will be included as fixed effects in the model. The following covariance structures and random effects will be considered: Marginal Unstructured, Marginal Variance Components, Marginal Compound Symmetry, Variance Components with Random Intercept, Unstructured with Random Intercept and Slope, Compound Symmetry with Random Intercept and Slope, Spatial Linear with Random Intercept and Slope. Choice of final model will be based on minimum AIC.

The dependent variable: change from Visit 3 at each *post-baseline interval*, i.e.: Change over post-baseline interval 1: (visit 7 –visit 3) Change over post-baseline interval 2: (visit 11-visit 3) Change over post-baseline interval 3: (Visit 15-Visit 3), for Cohort 1 only Change post-baseline interval 4: (Visit 19-Visit 3), for Cohort 1 only

Covariates are :

- Fixed effects:
 - Baseline interval change (Visit 3 Visit 2)
 - Treatment category (Dose= "5mg/kg", "5 + 40 mg/kg", "20mg/kg" or "40mg/kg")
 - o Time coded as Interval Indicator
 - Treatment category by time interaction
- Random effects:
 - Choice among Marginal Model, Random Intercept Model, and Random Intercept and Slope are selected based on the minimum AIC

Model-estimated change over each post-baseline interval with, 95% two-sided confidence intervals, will be displayed in tabular format.

For each dose level graphical displays will show model-based estimates of change in the mean functional measure from visit 3 at each visit and corresponding confidence intervals derived from the model.

Additionally a completer analysis will also be conducted as a sensitivity analysis for the missing data handling under the mixed effects modeling. The completer analysis will only

include subjects that completed all assessments at the last scheduled visit using the same longitudinal mixed effects model as the primary analysis.

Transformation of the data will be considered if model assumptions are not met.

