Table		Mean Maximal Expiratory Pressure (MEP)	Completer Population
		Mixed Model Repeated Measures (MMRM) of Change from	
	Table 14.1.1.100	Baseline	
Figure	Figure 14.1.1.22	Plot of Mean Absolute Value on Expiratory Pressure (MEP)	FAS
Figure		Plot of Mean Change from Baseline on Maximal Expiratory	FAS
	Figure 14.1.1.23	Pressure (MEP)	
Table	T 11 14 1 1 101	Summary of absolute value for Muscle Strength BY Manual	FAS
Table	Table 14.1.1.101	Muscle Test (MMT) and Hand-Hels dynamometry	EAC
Table	Table 14.1.1.102	Mean Change from Baseline for Muscle Strength BY Manual Muscle Test (MMT) and Hand-Hels dynamometry	FAS
Table	14010 14.1.1.102	Muscle Strength BY Manual Muscle Test (MMT) and	FAS
1 abic		Hand-Hels dynamometry	TAS
		Mixed Model Repeated Measures (MMRM) of Change from	
	Table 14.1.1.103	Baseline	
Table		Mean Muscle Strength BY Manual Muscle Test (MMT) and	Completer Population
		Hand-Hels dynamometry	
		Mixed Model Repeated Measures (MMRM) of Change from	
	Table 14.1.1.104	Baseline	
Listing	T 11 14 1 1 105	Listing of Manual Muscle Test (MMT) and Hand-Helded	FAS
T *	Table 14.1.1.105	dynamometry (Manual Muscle Test)	TAC
Listing		Listing of Manual Muscle Test (MMT) and Hand-Helded	FAS
	Table 14.1.1.106	dynamometry (Hand Held Myometry)	
Figure	Eigene 14 1 1 24	Plot of Mean Absolute Value on Muscle Strength BY Manual	FAS
Figure	Figure 14.1.1.24	Muscle Test (MMT) and Hand-Hels dynamometry Plot of Mean Change from Baseline on Muscle Strength BY	FAS
Figure	Figure 14.1.1.25	Manual Muscle Test (MMT) and Hand-Hels dynamometry	газ
Table	Table 14.1.1.107	Total Score for InQol	FAS
Table	Table 14.1.1.108	InQol: Summary Statistics for Weakness Symptom	FAS
Table	Table 14.1.1.109	InQol: Summary Statistics for Locking Symptom	FAS
Table	Table 14.1.1.110	InQol: Summary Statistics for Pain Symptom	FAS
Table	Table 14.1.1.111	InQol: Summary Statistics for Fatigue Symptom	FAS
Table		SF-36 Questionnaire : Listing of Physical and Mental	FAS
	Table 14.1.1.112	Components	
		GDF-8 Concentration	
Table	T 11 1411110	Serum Total GDF-8 Concentration (NG/ML) versus Time	
L	Table 14.1.1.113	Listing	l

1	1	
Figure		Individual Serum Total GDF-8 Concentration (NG/ML) -
	Figure 14.1.1.25	Time Plot by Cohort (Linear Scale)
Figure		Individual Change from Baseline of Serum Total GDF-8
	Figure 14.1.1.26	Concentration (NG/ML) - Time Plot by Cohort (Linear Scale)
Table	Table 14.1.1.114	Serum Total GDF-8 (NG/ML) versus Time Summary

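### SAP section 8 announces eight active-versus-lead-in tests, but the only secondary model (SAP 8.2.2) has no lead-in level and gives no active-minus-lead-in contrast or standard error

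*SAP*

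**What the plan says.** SAP section 8 divides each treatment period into 16-week intervals: weeks 17-32 and 33-48 in every cohort, and also 49-64 and 65-80 in Cohort 1. It pools the three cohorts' lead-in periods: "they are combined together to form a placebo group which will be used as a comparison group, testing against active treatments". It adds: "There will be a total of 20 subjects in the placebo group". It ends: "To conclude there will be 8 statistical tests". It names no test statistic, contrast, standard error or significance level.

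SAP 8.1 says that the methods for the primary and all secondary endpoints "are described in detail in Section 8.2.1 and Section 8.2.2 below".

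SAP 8.2.2 then gives a single mixed model for FVC, strength, timed function tests and patient-reported outcomes:

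- **Fixed effects:** "The change over the lead-in period, treatment, time and treatment by time interaction and will be included as fixed effects in the model". The treatment categories are 5, 5 + 40, 20 and 40 mg/kg. The lead-in change is Visit 3 minus Visit 2.
- **Outcomes:** all are measured from Visit 3, for example "Change over post-baseline interval 2: (visit 11-visit 3").
- **Output:** "Model-estimated change over each post-baseline interval with, 95% two-sided confidence intervals, will be displayed in tabular format".

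Appendix 1 titles the mixed-model tables as change from baseline. None is titled as a comparison with lead-in or placebo. For the questionnaires it lists descriptive displays such as "InQol: Summary Statistics for Weakness Symptom" and a listing for SF-36.

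**The concern.** The protocol (1.11 Study Design Rationale) includes the lead-in so that change before, during and after treatment can be compared. This open-label trial has no concurrent control, so the eight tests are the only planned comparison with untreated change. If the cited section does not define them, two statisticians could both follow the SAP and report different standard errors, and so different p-values, for the same test. The 8.2.2 confidence intervals cannot stand in for the tests, because they compare change with zero and not with lead-in change.

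The comparator is also not a separate group. Every active subject is one of the 20 lead-in subjects, and Visit 3 closes the lead-in and opens the first active interval. Section 8 does not mention this dependence.

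**Working it through.** **1. Reproduce the plan's counts.** Tests: 4 (Cohort 1) + 2 (Cohort 2) + 2 (Cohort 3) = 8. Lead-in subjects: 4 + 8 + 8 = 20. Both agree with section 8.

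**2. Set section 8 beside 8.2.2.** By the scheduled days, Visit 2 is Day -111 and Visits 3, 7, 11, 15 and 19 are Days 1, 113, 225, 337 and 449.

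| Test interval | Section 8 span | Per-interval change | 8.2.2 outcome and its span |
|---|---|---|---|
| 1 | 16 weeks | V7-V3 | V7-V3, 112/7 = 16 weeks |
| 2 | 16 weeks | V11-V7 | V11-V3, 224/7 = 32 weeks |
| 3 (Cohort 1) | 16 weeks | V15-V11 | V15-V3, 336/7 = 48 weeks |
| 4 (Cohort 1) | 16 weeks | V19-V15 | V19-V3, 448/7 = 64 weeks |
| Lead-in | 16 weeks | V3-V2 | covariate only |

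The model fills eight treatment-by-interval cells, so it supplies the active side. Increments such as V11-V7 can be recovered as differences of cumulative means. The lead-in side has no modelled mean or variance.

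**3. Standard error of a two-group test.** Let s be the SD of a 16-week change, assumed equal in all intervals, and r the within-subject correlation of lead-in and active change. The documents give neither, so r is shown from -0.5 to +0.5. With n active subjects among the 20:

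- true variance = s²(1/n + 1/20 - 2r/20)
- independent-groups variance = s²(1/n + 1/20)

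The true size of a test at an assumed nominal 5% is 2[1 - Φ(1.96/ratio)], by normal approximation.

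| n | r | True variance/s² | Independent variance/s² | SE ratio | True size |
|---|---|---|---|---|---|
| 8 | -0.5 | 0.225 | 0.175 | 1.134 | 8.4% |
| 8 | 0 | 0.175 | 0.175 | 1.000 | 5.0% |
| 8 | +0.5 | 0.125 | 0.175 | 0.845 | 2.0% |
| 4 | -0.5 | 0.350 | 0.300 | 1.080 | 7.0% |
| 4 | 0 | 0.300 | 0.300 | 1.000 | 5.0% |
| 4 | +0.5 | 0.250 | 0.300 | 0.913 | 3.2% |

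**4. Where r = -0.5 would arise.** With independent visit error of variance σ² and nothing else, V3-V2 and V7-V3 each have variance 2σ² and covariance -σ², so r = -0.5. Later intervals do not share Visit 3, so r = 0. Visit error alone therefore gives r = -0.5 in three of the eight tests. Lasting individual rates of progression push r upward.

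**5. Standard error if 8.2.2 is used directly.** Suppose the observed lead-in mean is subtracted, as a fixed number, from a covariate-adjusted active mean. With equal SDs the covariate slope is about r, so:

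- nominal variance = s²(1 - r²)/n
- true variance = s²[(1 - r²)/n + (1 - r)²/20]
- SE ratio = √[1 + n(1 - r)/(20(1 + r))]

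For n = 8 the ratio is √2.2 = 1.48 at r = -0.5, √1.4 = 1.18 at r = 0, and √1.133 = 1.06 at r = +0.5. This route understates the standard error over the whole range.

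**6. Patient-reported outcomes.** In the protocol's Schedule of Activities (Tables 1 and 2), InQoL and SF-36 are not marked at Visits 2, 7 or 15. Visit 3 minus Visit 2 is therefore missing for every subject, and the outcomes at intervals 1 and 3 do not exist.

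**The case against.** **A statistician can build the contrast by hand.** This is partly true. Active increments can be recovered, and a point difference from the observed lead-in mean can be formed. But the SAP does not say which standard error goes with it, and steps 3 and 5 give different answers.

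**Section 8 describes an ordinary two-group test, which is the natural reading.** This stands. On that reading the error is modest and can go either way: too liberal at negative r, exact at r = 0, too conservative at positive r. A reader might infer that the eight tests generally overstate significance. The documents do not support that, because they give no r, and visit error alone affects only interval 1.

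**8.2.2 compares 32 to 64 weeks of treatment with a 16-week lead-in.** A reader might infer this from the word interval on cumulative outcomes. The documents do not support it. Section 8 fixes separate 16-week spans for the tests, 8.2.2 states openly that its outcome is change from Visit 3, and neither section orders those outcomes to be set against the lead-in. The label is loose wording.

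**The questionnaires are a slip.** Appendix 1 plans only descriptive displays for them, so this part is a wording error in 8.2.2. The model still cannot be fitted for them as written.

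**Little depends on these tests.** This also stands. The primary objective is safety, no sample size was calculated (protocol 9.1), the escalation criteria (protocol 3.5.1) do not use these tests, and intervals 3 and 4 rest on four subjects.

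**Conclusion.** The inconsistency is real and should be fixed. The section cited for the method does not define the eight tests: it has no lead-in level, no active-minus-lead-in contrast and no matching standard error. A plain two-group test ignores the overlap of subjects. Its true standard error is 13% (n = 8) or 8% (n = 4) larger than assumed at r = -0.5, equal at r = 0, and 15% or 9% smaller at r = +0.5. Subtracting the lead-in mean as fixed from the 8.2.2 adjusted mean understates the standard error by a factor of 1.06 to 1.48 for n = 8.

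These sizes rest on an assumed range of r, equal SDs across intervals, a 5% level that section 8 does not state, and the normal approximation. The 16-week spans are nominal, since the protocol allows a longer Cohort 2 lead-in and a longer gap before Visit 11 in Cohort 1. SAP Figure 1 is not shown in the available text, so nothing is inferred from it. The definitional gap depends on none of the numerical assumptions. Its consequence is limited, because efficacy is secondary.

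**What to change.** Reconcile SAP section 8 with 8.2.2.

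- For strength, timed-function and pulmonary measures, specify one repeated-measures model for the eight tests. Use the per-interval changes (V3-V2, V7-V3, V11-V7; in Cohort 1 also V15-V11 and V19-V15) or the observed values at those visits.
- Make untreated lead-in a level of treatment. With per-interval changes, use a within-subject covariance that allows negative correlation between adjacent changes. Do not also enter the lead-in change as a covariate in this model.
- List the eight contrasts in Appendix 1.
- Keep 8.2.2 as the change-from-baseline analysis, and relabel its outcomes as cumulative change from Visit 3.
- Take InQoL and SF-36 out of the lead-in-adjusted model and out of the eight tests.

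Alternatively, delete the eight tests from section 8 if they are not wanted; the relabelling and the InQoL and SF-36 correction in 8.2.2 are still needed.

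The cost is SAP wording, one added model and one table per endpoint. The strength, timed-function and pulmonary measures are already scheduled at every visit required, so no new data are needed.

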8.2.3. PK Analyses

8.2.3.1. Concentrations below the limit of quantification

In all data presentations (except listings), concentrations below the limit of quantification (BLQ) will be set to zero. (In listings BLQ values will be reported as "<LLQ", where LLQ will be replaced with the value for the lower limit of quantification.)

8.2.3.2. Deviations, missing concentrations and anomalous values

In summary tables and plots of the median values at each time point, statistics will be calculated having set concentrations to missing if 1 of the following cases is true:

- 1. A concentration has been collected as ND (i.e. not done) or NS (i.e. no sample),
- 2. A deviation in sampling time is of sufficient concern or a concentration has been flagged anomalous by the pharmacokineticist.

Note that summary statistics will not be presented at a particular time point if more than 50% of the data are missing.

8.2.3.3. Pharmacokinetic parameters

Nominal PK sampling times will be used in the derivation of PK parameters.

If a PK parameter cannot be derived from a subject's concentration data, the parameter will be coded as NC (i.e. not calculated). (Note that NC values will not be generated beyond the day that a subject discontinues.)

In summary tables, statistics will be calculated by setting NC values to missing; and statistics will not be presented for a particular treatment if more than 50% of the data are NC. For statistical analyses (i.e. analysis of variance), PK parameters coded as NC will also be set to missing.

If an individual subject has a known biased estimate of a PK parameter (due for example to an unexpected event such as incomplete administration of the IV infusion dose), this will be footnoted in summary tables and will not be included in the calculation of summary statistics.

The PK parameters will be listed and summarized for subjects in the PK parameter analysis set. Parameters will be summarized by cohort and dose. Each PK parameter will include the set of summary statistics as specified in the table below:

Parameter	Summary Statistics
Cmax, Ctrough,	N, arithmetic mean, median, cv%, standard deviation, minimum, maximum, geometric mean, geometric CV%

Table 3.PK Parameters

8.2.3.4. PK Concentrations

To assess the PK profile of PF-06252616, PK concentrations will be listed, summarized and plotted for subjects in the PK analysis set, where missing and BLQ values will be handled as detailed in Section 8.2.4.2.

Presentations for PF-06252616 will include:

- A listing of all concentrations sorted by dose, subject ID, cohort and nominal time postdose. The listing of concentrations will include the actual sample collection times, and the time of dosing. Deviations from the nominal time will be given in a separate listing.
- A summary of concentrations by cohort, dose and nominal time postdose, where the set of statistics will include n, mean, median, standard deviation, coefficient of variation (cv), minimum, maximum and the number of concentrations above the lower limit of quantification.
- Median trough (predose) concentrations against nominal dosing week by cohort and dose. Individual subject trough concentrations will also be plotted. Linear scale.
- Median concentrations at the end of infusion (nominally at 2 hour post start of infusion) against nominal dosing week by cohort and dose, as described above for trough concentrations. Individual subject end of infusion concentrations will also be plotted. Linear scale.

The range for the x-axes of these plots will be decided on review of the data, and will depend on how long PF-06252616 concentration is quantifiable in the matrix.

For summary statistics and median plots by sampling time, the nominal PK sampling time will be used. For individual subject plots by time, the actual PK sampling time will be used.

8.2.4. GDF-8 Analysis

8.2.4.1. Deviations, missing concentrations and anomalous values

In summary tables and plots of the median values at each time point, statistics will be calculated having set concentrations to missing if 1 of the following cases is true:

1. A concentration has been collected as ND (i.e. not done) or NS (i.e. no sample),

2. A deviation in sampling time is of sufficient concern or a concentration has been flagged anomalous by the pharmacokineticist.

Note that summary statistics will not be presented at a particular time point if more than 50% of the data are missing.

8.2.4.2. GDF-8 Concentration

To assess the PD profile of PF-06252616, GDF-8 concentrations will be listed, summarized and plotted for subjects in the PD analysis set, where missing the data will be handles as outlined in Section 8.2.5.1.

- A listing of all concentrations sorted by dose, subject ID, cohort and nominal time postdose. The listing of concentrations will include the actual sample collection times, and the time of dosing. Deviations from the nominal time will be given in a separate listing.
- A summary of concentrations by dose, cohort and nominal time postdose, where the set of statistics will include n, mean, median, standard deviation, coefficient of variation (cv), minimum, maximum and the number of concentrations above the lower limit of quantification.
- Median total GDF-8 concentrations and Change from Baseline against nominal time postdose by cohort and Dose. Linear scale.
- Mean total GDF-8 concentrations and Change from Baseline against nominal time postdose by cohort and Dose. Linear scale.
- Individual total GDF-8 concentrations and Change from Baseline against actual time postdose by cohort and Dose (including all subjects). Linear scale.

The range for the x-axes of these plots will be decided on review of the data, and will depend on how long GDF-8 concentration is quantifiable in the matrix.

For summary statistics and median plots by sampling time, the nominal GDF-8 sampling time will be used. For individual subject plots by time, the actual GDF-8 sampling time will be used.

8.2.5. Other Analyses

8.2.5.1. Exploratory Analyses

All exploratory endpoints, including the pharmacologic and health outcome endpoints will be summarized by treatment group. Additional analyses may be performed to understand the relationship between these endpoints and treatment.

Any population PK/PD analysis conducted will be reported separately.

Additionally, data permitting, relationships between PF-06252616 PK, GDF-8, imaging data (DXA, MRI), functional assessment, immunogenicity and any safety signals may be explored.

APPENDIX 1.

Planned Data Display

Item	Number	Title	Population
		ENROLLMENT AND DISPOSITION	
Table	Table 14.1.1.1	Subject Evaluation Groups by Cohort	All Enrolled Subjects
Listing	Table 14.1.1.2	Subject Evaluation Groups	All Enrolled Subjects
Listing	Table 14.1.1.3	Subject Discontinuation	All Enrolled Subjects
		DEMOGRAPHICS	
Table	Table 14.1.1.4	Subject Demographics and Baseline Characteristics	FAS
Listing	Table 14.1.1.5	Subject Demographics and Baseline Characteristics	FAS
Listing	Table 14.1.1.6	Clinical Significance of Physical Examination	FAS
		Study Drug	
Table	Table 14.1.1.7	Summary of Number of Subjects by Cohort and Dose Level	FAS
Listing	Table 14.1.1.8	Administration Schedule	FAS
Listing	Table 14.1.1.9	Infusion Site Assessment	FAS
Listing	Table 14.1.1.10	Dose Administration by Dose Level and Visit	FAS
Listing	Table 14.1.1.11	Dose Administration by Dose Level, Cohort and Visit	FAS
Listing	Table 14.1.1.12	Dose Administration by Cohort, Total and Visit	FAS
		Safety	
Table		Treatment-Emergent Adverse Events (All Causalities) by	FAS
	Table 14.1.1.13	Dose Level and Cohort	
Table		Treatment-Emergent Adverse Events (All Causalities) by	FAS
	Table 14.1.1.14	Cohort and Total	
Table		Incidence and Severity of Treatment-Emergent Adverse	FAS
	Table 14.1.1.15	Events by Dose Level and Cohort (All Causalities)	
Table		Incidence and Severity of Treatment-Emergent Adverse	FAS
	Table 14.1.1.16	Events by Cohort and Total (All Causalities)	
Table		Treatment-Emergent Adverse Events (Treatment Related) by	FAS
	Table 14.1.1.17	Dose Level and Cohort	
Table		Treatment-Emergent Adverse Events (Treatment Related) by	FAS
	Table 14.1.1.18	Cohort and Total	
Table		Incidence and Severity of Treatment-Emergent Adverse	FAS
	Table 14.1.1.19	Events by Dose Level and Cohort (Treatment Related)	
Table		Incidence and Severity of Treatment-Emergent Adverse	FAS
	Table 14.1.1.20	Events by Cohort and Total (Treatment Related)	
Table	Table 14.1.1.01	Serious Adverse Events by System Organ Class by Dose	FAS
Takl	Table 14.1.1.21	Level and Cohort (All Causalities)	EAC
Table	Table 14 1 1 22	Serious Adverse Events by System Organ Class by Cohort	FAS
Table	Table 14.1.1.22	and Total (All Causalities) Serious Adverse Events by System Organ Class by Dose	FAS
Table	Table 14.1.1.23	Level and Cohort (Treatment Related)	TAS
Listing	Table 14.1.1.23	Discontinuations Due to Adverse Events	FAS
Listing	Table 14.1.1.24	Adverse Events	FAS
Listing	Table 14.1.1.25	Individual Listing of Deaths	FAS
Listing	Table 14.1.1.20 Table 14.1.1.27	Serious Adverse Events	FAS
Listing	Table 14.1.1.27 Table 14.1.1.28	Treatment Related Serious Adverse Events	FAS
Listing	14010 14.1.1.20	Clinical Laboratory	
T-11			EAG
Table	Table 14.1.1.20	Incidence of Laboratory Test Abnormalities (without Regard	FAS
Takl	Table 14.1.1.29	to Baseline Abnormality) by Dose Level and Cohort	EAC
Table	Table 14.1.1.30	Serum Iron Indices (Total Iron Binding Capacity, Serum Iron,	FAS

	1		
		Serum Ferritin, % Transferrin Saturation) - Observed values,	
		Change and Percent Change from Baseline	
Table		Categorical Summary of Serum Ferritin, Serum Iron and %	FAS
	Table 14.1.1.31	Transferrin Saturation	
Table		Serum Iron Indices (Total Iron Binding Capacity, Serum Iron,	FAS
	Table 14.1.1.32	Serum Ferritin, % Transferrin Saturation)	
Table		Serum Ferritin, Serum Total Iron, and % Transferrin	FAS
		Saturation Values Meeting Categorical Summarization	
	Table 14.1.1.33	Criteria	
Table		Serum PF-06252616 Concentration (ng/mL) versus Time	FAS
	Table 14.1.1.34	Summary	
Listing	Table 14.1.1.35	Laboratory Abnormalities, by Cohort and Subject	FAS
Listing	Table 14.1.1.36	Laboratory Abnormalities, by Dose Level and Subject	FAS
Listing	Table 14.1.1.37	Laboratory Abnormalities, by Cohort, Dose Level and Test	FAS
		Vital Signs	
Figure	Figure 14.1.1.1	Vital Signs Absolute Values by Dose level	FAS
Figure	Figure 14.1.1.2	Vital Signs Change from baseline by Dose Level	FAS
		Electrocardiogram	
Table	Table 14.1.1.38	Mean Baseline and Mean Changes from Baseline	FAS
	1 able 14.1.1.38	Categorical Summary of Post-Baseline ECG Data - Absolute	FAS
Table	T_{a} h_{a} $14.1.1.20$	Values	FAS
Table	Table 14.1.1.39	Categorical Summary of Post-Baseline ECG Data - Increases	FAS
lable	T-11-14-1-1-40		FAS
T 11	Table 14.1.1.40	from Baseline	TAG
Table	T 11 14 1 1 41	Number (%) of Subjects with Single Uncorrected QT Values	FAS
T 11	Table 14.1.1.41	Greater than or Equal to 500 msec	T +0
Table	Table 14.1.1.42	ECG Change from Baseline	FAS
Table	Table 14.1.1.43	ECG Qualitative Results	FAS
Table	T 11 111111	ECG Post-Baseline Values Meeting Categorical	FAS
	Table 14.1.1.44	Summarization Criteria	
Figure		QTcF Interval (Fridericia's Correction) values over Time by	FAS
		Dose Level - Box Plots	
	Figure 14.1.1.3		
Figure		QTcF Interval (Fridericia's Correction) values change from	FAS
		baseline over Time by Dose Level - Box Plots	
	Figure 14.1.1.4		
Figure		QT versus Heart Rate by Dose Level	FAS
	Figure 14.1.1.5		
		Cardiac MRI/Echocardiogram	
Table		Shift Table of Left Ventricular Ejection Fraction over time by	FAS
	Table 14.1.1.45	and Echocardiogram	
Table		Mean absolute and percent change from baseline in Left	FAS
	Table 14.1.1.46	Ventricular Ejection Fraction (LVEF)	
Table		Mean absolute and percent change from baseline in Left	FAS
10010	Table 14.1.1.47	Ventricular End Systolic Volume (LVESV)	1110
Listing	Table 14.1.1.48	Echoardiagram	FAS
Listing		Liver MRI	
Table			EAS
Table	Table 14 1 1 40	Summary of Average R2* Values and Percent Change from Pasaling by Vicit and Magnet Field Strength	FAS
Table	Table 14.1.1.49	Baseline by Visit and Magnet Field Strength	EAS
Table	Table 14.1.1.50	Summary of Iron Accumulation	FAS
Table	Table 14.1.1.51	Number (%) of Liver Enzyme Abnormalities by dose level	FAS
Listing	Table 14.1.1.52	Liver Enzyme Abnormalities	FAS
Listing	Table 14.1.1.53	Liver MRI	FAS
Listing	Table 14.1.1.54	Liver MRI Abnormalities: R2* Elevations	FAS

		DVA	FAS
		DXA	
Table	Table 14.1.1.55	Bone Mineral Density over Time by Treatment (Whole Body)	FAS
Table	Table 14.1.1.56	Bone Mineral Density over Time by Treatment (Hip)	FAS
Table		Bone Mineral Density over Time by Treatment (Lumbar	FAS
	Table 14.1.1.57	Spine)	
Listing	Table 14.1.1.58	DXA	FAS
		Concomitant Medication	
Listing	Table 14.1.1.59	Concomitant Medications	FAS
		CSSR	
Listing		C-SSRS by Time (Baseline/screen Version and Since last	FAS
U	Table 14.1.1.60	Visit)	
Listing		C-SSRS by Time (Baseline/screen Version and Since last	FAS
0	Table 14.1.1.61	Visit) – Cont.	
		ADA	
Table	Table 14.1.1.62	Anti-drug Antibodies (ADA) Status by Dose Level	FAS
		Secondary Endpoints:	
Table	Table 14.1.1.63	Summary of absolute value for Forced Vital Capcity (FVC)	FAS
Table	Table 14.1.1.64	Mean Change from Baseline for Forced Vital Capcity (FVC)	FAS
Table	14010 14.1.1.04	Mean Forced Vital Capcity (FVC)	FAS
Table		Mixed Model Repeated Measures (MMRM) of Change from	TAD
	Table 14.1.1.65	Baseline	
Table	14010 14.1.1.05	Mean Forced Vital Capcity (FVC)	Completer Population
Table		Mixed Model Repeated Measures (MMRM) of Change from	
	Table 14.1.1.66	Baseline	
Figure	Figure 14.1.1.6	Plot of Mean Absolute Value on Frorced Vital Capcity	FAS
Figure	Figure 14.1.1.7	Plot of Mean Change from Baseline on Frorced Vital Capcity	FAS
Table	1 igure 14.1.1.7	Summary of absolute value for Performance of Upper	FAS
Table	Table 14.1.1.67	Limb(PUL)	1710
Table	10010 1 1.1.1.07	Mean Change from Baseline for Performance of Upper	FAS
Tuble	Table 14.1.1.68	Limb(PUL)	1110
Table		Mean Performance of Upper Limb(PUL)	FAS
		Mixed Model Repeated Measures (MMRM) of Change from	
	Table 14.1.1.69	Baseline	
Table		Mean Performance of Upper Limb(PUL)	Completer Population
		Mixed Model Repeated Measures (MMRM) of Change from	1 1
	Table 14.1.1.70	Baseline	
Table	Table 14.1.1.71	Listing of Performance of Upper Limb	FAS
Listing		Listing of items, Description and Scores Performance of	
	Table 14.1.1.72	Upper Limb	
Figure		Plot of Mean Absolute Value on Performance of Upper	FAS
	Figure 14.1.1.8	Limb(PUL)	
Figure		Plot of Mean Change from Baseline on Performance of Upper	FAS
	Figure 14.1.1.9	Limb(PUL)	
Table	Table 14.1.1.73	Summary of absolute value for Timed Up & Go (TUG)	FAS
Table	Table 14.1.1.74	Mean Change from Baseline for Timed Up & Go (TUG)	FAS
Table		Mean Timed Up & Go (TUG)	FAS
		Mixed Model Repeated Measures (MMRM) of Change from	
	Table 14.1.1.75	Baseline	
Table		Mean Timed Up & Go (TUG)	Completer Population
		Mixed Model Repeated Measures (MMRM) of Change from	
	Table 14.1.1.76	Baseline	

Figure	Figure 14.1.1.10	Plot of Mean Absolute Value on Timed Up & Go (TUG)	FAS
Figure	1 iguie 14.1.1.10	Plot of Mean Change from Baseline on Timed Up & Go	FAS
riguit	Figure 14.1.1.11	(TUG)	1110
Table	Table 14.1.1.77	Summary of absolute value for for10-meter walk/run (10MR)	FAS
Table	Table 14.1.1.78	Mean Change from Baseline for10-meter walk/run (10MR)	FAS
Table	14010 1 1111110	Mean 10-meter walk/run (10MR)	FAS
1		Mixed Model Repeated Measures (MMRM) of Change from	
	Table 14.1.1.79	Baseline	
Table		Mean 10-meter walk/run (10MR)	Completer Population
		Mixed Model Repeated Measures (MMRM) of Change from	1 1
	Table 14.1.1.80	Baseline	
Figure	Figure 14.1.1.12	Plot of Mean Absolute Value on 10-meter walk/run (10MR)	FAS
Figure	~	Plot of Mean Change from Baseline on 10-meter walk/run	FAS
0	Figure 14.1.1.13	(10MR)	
Table		Summary of absolute value for Two Minute Walk Test	FAS
	Table 14.1.1.81	(2MWT)	
Table		Mean Change from Baseline for Two Minute Walk Test	FAS
	Table 14.1.1.82	(2MWT)	
Table		Mean Two Minute Walk Test (2MWT)	FAS
		Mixed Model Repeated Measures (MMRM) of Change from	
	Table 14.1.1.83	Baseline	
Table		Mean Two Minute Walk Test (2MWT)	Completer Population
		Mixed Model Repeated Measures (MMRM) of Change from	
	Table 14.1.1.84	Baseline	
Figure		Plot of Mean Absolute Value on Two Minute Walk Test	FAS
	Figure 14.1.1.14	(2MWT))	
Figure		Plot of Mean Change from Baseline on Two Minute Walk	FAS
	Figure 14.1.1.15	Test (2MWT)	
Table	Table 14.1.1.85	Summary of absolute value for 4 Stair Climb (4SC)	FAS
Table	Table 14.1.1.86	Mean Change from Baseline for 4 Stair Climb (4SC)	FAS
Table		Mean 4 Stair Climb (4SC)	FAS
	T-11. 14 1 1 07	Mixed Model Repeated Measures (MMRM) of Change from	
Table	Table 14.1.1.87	Baseline	Commission Doministra
Table		Mean 4 Stair Climb (4SC) Mixed Model Repeated Measures (MMRM) of Change from	Completer Population
	$T_{abla} 141199$	Baseline	
Figure	Table 14.1.1.88 Figure 14.1.1.16	Plot of Mean Absolute Value on 4 Stair Climb (4SC)	FAS
Figure	Figure 14.1.1.16 Figure 14.1.1.17	Plot of Mean Change from Baseline on 4 Stair Climb (4SC)	FAS
Table	11guit 14.1.1.1/	Summary of absolute value for Forced Expiratory Volume in	FAS
1 able	Table 14.1.1.89	1 second (FEV1)	IAU
Table	1 4010 17.1.1.07	Mean Change from Baseline for Forced Expiratory Volume in	FAS
1 4010	Table 14.1.1.90	1 second (FEV1)	1710
Table	14010 1 11111.00	Mean Forced Expiratory Volume in 1 second (FEV1)	FAS
		Mixed Model Repeated Measures (MMRM) of Change from	
	Table 14.1.1.91	Baseline	
Table		Mean Forced Expiratory Volume in 1 second (FEV1)	Completer Population
		Mixed Model Repeated Measures (MMRM) of Change from	r ···· · · r
	Table 14.1.1.92	Baseline	
Figure		Plot of Mean Absolute Value on Forced Expiratory Volume	FAS
0	Figure 14.1.1.18	in 1 second (FEV1)	
Figure	 	Plot of Mean Change from Baseline on Forced Expiratory	FAS
0	E	Volume in 1 second (FEV1)	
	Figure 14.1.1.19		
Table	Figure 14.1.1.19		FAS
Table	Table 14.1.1.93	Summary of absolute value for Maximal Inspiratory Pressure (MIP)	FAS

		Pressure (MIP)	
Table		Mean Maximal Inspiratory Pressure (MIP)	FAS
Table		Mixed Model Repeated Measures (MMRM) of Change from	1710
	Table 14.1.1.95	Baseline	
Table		Mean Maximal Inspiratory Pressure (MIP)	FAS
		Mixed Model Repeated Measures (MMRM) of Change from	
	Table 14.1.1.96	Baseline	
Figure		Plot of Mean Absolute Value on Maximal Inspiratory	FAS
	Figure 14.1.1.20	Pressure (MIP)	
Figure		Plot of Mean Change from Baseline on Maximal Inspiratory	FAS
m 11	Figure 14.1.1.21	Pressure (MIP)	
Table	T-1-1-14-1-1-07	Summary of absolute value for Maximal Expiratory Pressure	FAS
Table	Table 14.1.1.97	(MEP) Mean Change from Baseline for Maximal Expiratory Pressure	FAS
Table	Table 14.1.1.98	(MEP)	ГАЗ
Table	14010 14.1.1.98	Mean Maximal Expiratory Pressure (MEP)	FAS
Table		Mixed Model Repeated Measures (MMRM) of Change from	1745
	Table 14.1.1.99	Baseline	
Table		Mean Maximal Expiratory Pressure (MEP)	Completer Population
		Mixed Model Repeated Measures (MMRM) of Change from	
	Table 14.1.1.100	Baseline	
Figure	Figure 14.1.1.22	Plot of Mean Absolute Value on Expiratory Pressure (MEP)	FAS
Figure		Plot of Mean Change from Baseline on Maximal Expiratory	FAS
	Figure 14.1.1.23	Pressure (MEP)	
Table	T 11 14 1 1 101	Summary of absolute value for Muscle Strength BY Manual	FAS
Table	Table 14.1.1.101	Muscle Test (MMT) and Hand-Hels dynamometry	EAC
Table	Table 14.1.1.102	Mean Change from Baseline for Muscle Strength BY Manual Muscle Test (MMT) and Hand-Hels dynamometry	FAS
Table	14010 14.1.1.102	Muscle Strength BY Manual Muscle Test (MMT) and	FAS
1 abic		Hand-Hels dynamometry	TAS
		Mixed Model Repeated Measures (MMRM) of Change from	
	Table 14.1.1.103	Baseline	
Table		Mean Muscle Strength BY Manual Muscle Test (MMT) and	Completer Population
		Hand-Hels dynamometry	
		Mixed Model Repeated Measures (MMRM) of Change from	
	Table 14.1.1.104	Baseline	
Listing	T 11 14 1 1 105	Listing of Manual Muscle Test (MMT) and Hand-Helded	FAS
T *	Table 14.1.1.105	dynamometry (Manual Muscle Test)	TAC
Listing		Listing of Manual Muscle Test (MMT) and Hand-Helded	FAS
	Table 14.1.1.106	dynamometry (Hand Held Myometry)	
Figure	Eigene 14 1 1 24	Plot of Mean Absolute Value on Muscle Strength BY Manual	FAS
Figure	Figure 14.1.1.24	Muscle Test (MMT) and Hand-Hels dynamometry Plot of Mean Change from Baseline on Muscle Strength BY	FAS
Figure	Figure 14.1.1.25	Manual Muscle Test (MMT) and Hand-Hels dynamometry	газ
Table	Table 14.1.1.107	Total Score for InQol	FAS
Table	Table 14.1.1.108	InQol: Summary Statistics for Weakness Symptom	FAS
Table	Table 14.1.1.109	InQol: Summary Statistics for Locking Symptom	FAS
Table	Table 14.1.1.110	InQol: Summary Statistics for Pain Symptom	FAS
Table	Table 14.1.1.111	InQol: Summary Statistics for Fatigue Symptom	FAS
Table		SF-36 Questionnaire : Listing of Physical and Mental	FAS
	Table 14.1.1.112	Components	
		GDF-8 Concentration	
Table	T 11 1411110	Serum Total GDF-8 Concentration (NG/ML) versus Time	
L	Table 14.1.1.113	Listing	l

1	1	
Figure		Individual Serum Total GDF-8 Concentration (NG/ML) -
	Figure 14.1.1.25	Time Plot by Cohort (Linear Scale)
Figure		Individual Change from Baseline of Serum Total GDF-8
	Figure 14.1.1.26	Concentration (NG/ML) - Time Plot by Cohort (Linear Scale)
Table	Table 14.1.1.114	Serum Total GDF-8 (NG/ML) versus Time Summary
